#### **d. Rationale for Study Design**

We propose a double-blinded randomized controlled trial to minimize bias and ensure similar baseline characteristics of the patients in each study group. Patients will be randomized to receive a pre-operative subacromial injection containing either bupivacaine with epinephrine, or bupivacaine alone. We will collect baseline characteristics of patients as well as potential confounding factors throughout and after the surgery to ensure that any difference in surgeon-rated visual clarity is a direct consequence of the intervention.

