## **5. STUDY DESIGN**

### **5.1. Summary of Study Design**

The study utilizes parallel groups with randomized assignments. Randomization will be performed prior to surgery and group designation will be placed within an opaque envelope in the patient's chart. The circulating nurse will prepare the pre-operative injection: study patients will receive an injection containing a total volume of 20 mL of bupivacaine with epinephrine (0.3 mL epinephrine in 30 mL of 0.5% bupivacaine) whereas control patients will receive an injection containing 20mL of 0.5% bupivacaine alone. The syringe will not be labeled, and the contents of the injection will not be disclosed to the surgeon to preserve blinding. The injection will be performed with an 18-gauge needle into the subacromial space via a posterior or lateral approach after positioning the patient in the beach chair position, but prior to prepping and draping. The first 10 liters of arthroscopic irrigation used during the case will contain a total of 10 mg of epinephrine (dilution 1:1000), then saline without epinephrine will be used for the remainder of the surgical procedure. Throughout the case, the mean arterial pressure of the patient will be monitored. At the conclusion of the surgical procedure, the surgeon will rate visual clarity on a visual analog scale from 0 to 10. We will also record changes in pump pressure from the initial pressure of 35mmHg during the surgical procedure. Finally, we will note any adverse events during or after the surgical procedure. In the unlikely event of an intra-operative or early post-operative adverse event that may be related to epinephrine administration, the presence or lack of epinephrine will be revealed to the anesthesiology team to ensure optimal treatment of the adverse event.

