## **6. METHODS AND ASSESSMENTS**

### **6.1. Randomization and Blinding**

Simple randomization of enrolled subjects will occur prior to surgical intervention. A certified random number generator will be accessed that will generate a number to assign to the enrolled patient. A research coordinator will bring the randomization envelopes on the day of surgery. Blinding of enrolled subjects will be performed to prevent bias from occurring based on patient expectations of the procedure. To reduce recall bias, group allocation will be kept concealed from the investigator until the completion of visual clarity scoring at the conclusion of each surgical procedure.

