### **8.5. Blinding**

Blinding of enrolled subjects will be performed to prevent bias from occurring based on patient expectations of the procedure. If desired, patients may learn of their study designation after completion of the surgeon-rated visual clarity score immediately post-operatively.

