#### UTHealth CTRC DSMP Checklist

- Primary and secondary outcome measures
  - o Primary: surgeon-rated visual clarity score (visual analog scale 0 to 10), changes in intra-operative arthroscopic pump pressure
  - o Secondary: mean arterial pressure intra-operatively, total operative time, adverse events intra-operatively or post-operatively
  - o Inclusion: patients 18 years of age or older who are able to provide informed consent and who are to undergo arthroscopic shoulder surgery in the seated upright (beach-chair) position requiring visualization of within the subacromial space.
  - o Exclusion: Are unable to provide informed consent, non-English speaker, have a history of adverse medication reaction to epinephrine, and who are having arthroscopic shoulder surgery that does not require visualization within the subacromial space or performed in the lateral position.
  - o Sample size: Thirty (n=30) subjects recruited from Texas will be sought for each group for a total enrollment of sixty (n=60). This is from a power analysis performed. The minimal clinically significant difference in visual acuity score (0-10) is 2 points, or 20%, as established in a prior study. In order to ensure 80% power at an alpha of 0.05, a minimum of 26 patients are needed in each study group.
- List of participating enrolling clinics or data collection centers
  - o Memorial Hermann Memorial City Medical Center
  - o Memorial Hermann Surgery Center West Houston
  - o Memorial Hermann Orthopedic & Spine Hospital
  - o Memorial Hermann Surgery Center
  - o UT Physicians Orthopedics – Texas Medical Center
  - o UT Physicians Orthopedics – Memorial City
- Projected timeline
  - o Based on historic clinic data for the principal investigator and co-investigators, we anticipate meeting our enrollment target around 12 weeks from opening enrollment. Once enrolled, subjects will be randomized into either the epinephrine or placebo group. Surgeon-rated visual clarity score will be obtained immediately post-operatively.
- Target population distribution (e.g., women, minorities, etc.)
  - o The target population distribution will be the typical patients that the principal investigator and co-investigators schedules and operates on here at the UT Health and Memorial Hermann Health systems. Randomization will ensure that both groups will have similar demographic backgrounds.
- Data acquisition and transmission

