  - o Clinical assessments and images will be uploaded and stored on Epic and Centricity as is standard. The recorded assessments and images will be stored for study use for at least six years, with all study related data stored in Redcap.
  - o Demographic data (name, age, gender, weight, race) will be collected from medical records and stored in Redcap.
  - o Surgical data (start and stop times for procedure, type of procedure performed, mean arterial pressure) will be recorded and stored in Redcap.

- Objective clinical data (adverse events) will be collected during the post-operative period with information collected stored in Redcap.
  - Subjective clinical data (surgeon-rated visual clarity score, surgeon-requested increase in arthroscopic irrigation pump pressure) will be recorded and stored in Redcap.
  - Imaging data (none)
- Data entry methods
  - A linking log and data collection form will be used to protect subjects' PHI. All data will be entered and stored in a Redcap project drive to ensure maximal security and anonymity.
- Data analysis plan
  - Demographic variables and diagnostic outcomes will be compared using t-test for continuous variables and chi-square or Fisher exact test for categorical variables. A Mann-Whitney rank sum test will be used to compare median visual clarity scores.
- Quality assurance plan
  - To maintain accuracy, consistency and completeness of data, periodic audits and self-assessments will be conducted. The data will be cross-checked by the study coordinator and the PIs to maintain quality control.
- Reporting mechanisms of AEs/SAEs to the IRB, FDA, and NIDA
  - The principal investigator will report all AEs and SAEs occurring in clinical investigations to the IRB according to the UTHSC-Houston IRB policy. A definition of what constitutes an AE or SAE can be found below in this document as well as within the study protocol.
    - AEs will be compiled and submitted on an annual basis to the IRB. Each AE will require review from the investigator as soon as identified.
    - SAEs will be reviewed by the investigator as soon as identified, and all SAEs will be reported to the IRB within 48 hours of identification.
- Reporting mechanisms of IRB actions to NIDA
  - No drugs are involved in this study, so reporting to the NIDA will not be necessary.
- Report of changes or amendments to the protocol

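### The blind is guaranteed only until each case's clarity score, so post-operative adverse events may be reported and graded with the arm known

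*Combined protocol and SAP*

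**What the plan says.** Section 1.2.d states the design: "We propose a double-blinded randomized controlled trial to minimize bias". Three places then describe the blind.

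- **Section 5.1 (surgeon).** The syringe is unlabeled and "the contents of the injection will not be disclosed to the surgeon to preserve blinding". No end point is given. The same section says "group designation will be placed within an opaque envelope in the patient" (the sentence goes on to name the chart). For an adverse event during or soon after surgery that may be related to epinephrine, "the presence or lack of epinephrine will be revealed to the anesthesiology team".
- **Section 6.1 (investigator).** "group allocation will be kept concealed from the investigator until the completion of visual clarity scoring at the conclusion of each surgical procedure".
- **Section 8.5 (patient).** On request, "patients may learn of their study designation after completion of the surgeon-rated visual clarity score immediately post-operatively".

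On outcomes, the data and safety monitoring checklist in Section 9.3 lists "Secondary: mean arterial pressure intra-operatively, total operative time, adverse events intra-operatively or post-operatively". On timing, it says "Objective clinical data (adverse events) will be collected during the post-operative period". Section 9.2 requires events to be recorded whether the patient reports them or they are found on examination. It grades severity in three categories and has the investigator assign causality.

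**The concern.** A blind protects an outcome only if it lasts until that outcome has been reported and judged. Here it may be lifted, for patient and investigator alike, while one listed outcome is still open. Sections 6.1 and 8.5 give the patient's expectations as the reason for blinding patients. That reason applies equally to a patient deciding after surgery whether to mention a symptom. On the investigator's side, the severity definitions turn partly on how well an event is tolerated and how much it concerns the patient, and causality is a judgement. Knowing whether the injection contained epinephrine could influence both.

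A lesser point concerns the surgeons. Section 5.1 sets no end to their blind, while Section 6.1 sets one for the investigator, case by case. The checklist describes the study population as patients on whom the principal investigator and co-investigators operate, so these roles overlap. As written, a surgeon could learn the arms of finished cases while still rating clarity, a subjective primary outcome, in later ones. No section says that surgeons are told.

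**Working it through.** The plan states no figure on this point, and the sample-size calculation does not bear on it. The check sets the release point against the time at which each outcome is generated.

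**Inputs**

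- Outcomes (Section 9.3 checklist): 2 primary + 3 secondary = 5.
- Release of the blind (Sections 6.1 and 8.5): completion of the clarity score at the end of each operation.
- Planned enrollment (Sections 3.1 and 11.1): 2 × 30 = 60 patients.

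**Each outcome against the release point**

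| Outcome | Role | Generated by the time of scoring? |
|---|---|---|
| Visual clarity score | Primary | Yes; it defines the release |
| Pump-pressure changes | Primary | Yes |
| Intra-operative mean arterial pressure | Secondary | Yes |
| Total operative time | Secondary | Yes |
| Adverse events, intra- or post-operative | Secondary | Not the post-operative part |

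Four of 5 outcomes are generated by the time of scoring, and 5 − 4 = 1 remains open. Within that outcome, intra-operative events occur while the blind holds, although no section requires them to be graded before disclosure. The upper limit on exposed patients is total enrollment, 60. The number actually exposed depends on who is told and who then has an event, and the documents give neither.

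**Is the blind extended elsewhere?** Sections 5.1, 6.1, 8.5, 9.1 to 9.3 and 11.2 were read for this. None extends it to the end of adverse-event collection, the last patient or database lock. None names a blinded adverse-event assessor or requires grading before disclosure. Section 5.1 gives no duration for the surgeon's blind, so it does not override the end point in Section 6.1. Its emergency provision names only the anesthesiology team.

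**Can the release reach the two primary outcomes?** Each patient's own clarity score and pump-pressure record precede the release of that patient's arm. Simple randomization (Section 6.1) means that the arms of finished cases do not predict the next one. Bias is therefore shown for 0 of the 2 primary outcomes.

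**The case against.** The strongest reply accepts the reading of the text and disputes its consequence.

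- **The wording is permissive.** Section 6.1 sets a minimum period of concealment and does not order disclosure, and Section 8.5 applies only to patients who ask. This is correct, which is why the point is put as a possibility. A blind that may be lifted before an outcome is complete is still not guaranteed for that outcome.
- **Few events will be exposed.** Section 6.3 requires no visit after surgery and plans no follow-up, and Section 9.3 expects cardiovascular events to be very rare. This stands and reduces the exposure. It does not blind the events that are captured.
- **Section 9.2 already guards against elicitation bias**, by non-leading questioning and written severity definitions. These help, but they do not conceal the arm from the patient or the grader.
- **Adverse events are labeled objective, and Section 11.2 plans no comparison of severity or causality grades.** The second half is true and limits what is at stake. The label does not fit events that patients report and investigators grade. Section 11.2 also starts an early analysis after a serious event judged medication-related, and that is itself a causality call.
- **Causality is defined against the study procedure, which both arms undergo.** This narrows the concern without removing it, because the lead-in in Section 9.2 also refers to the study product.
- **Sections 5.1 and 6.1 are compatible, and a narrower fix would do:** blinding until each patient's events are graded, or a blinded grader. The two sections can be read together, and the narrower fix would protect adverse events. It would not stop surgeons learning the arms of finished cases while still rating later ones. Holding the blind to database lock covers both at almost no extra cost.

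**Conclusion.** The concern holds and is minor. Sections 6.1 and 8.5 state a release rule that ends the guaranteed blind before one of the five listed outcomes is complete, and nothing else in the document extends it. Exposure is confined to post-operative adverse events reported or graded after scoring, in at most 60 patients and probably far fewer. No bias is demonstrated in either primary outcome, and neither the size nor the direction of any bias in adverse events can be derived from the documents.

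The reading of the text is firm. An actual effect would need three things that the documents do not show: disclosure takes place, a post-operative event follows or remains to be graded, and knowledge of the arm changes the report or the grade.

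**What to change.** Amend Sections 5.1, 6.1 and 8.5 to give one common end point: patients, surgeons and the investigators who judge adverse events stay blinded until the last patient's data are complete and the database is locked. In support of that:

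- Keep the chart envelope sealed after scoring, or have it held by unblinded study staff who neither rate clarity nor judge adverse events. The circulating nurse who prepares the syringe does not disclose the arm.
- Leave the emergency disclosure in Section 5.1 as written.
- State that the safety monitor or DSMB may see allocation for the reports at 30 and 60 patients (Section 9.3) and for the early analysis in Section 11.2.
- Log every unblinding with its date, its reason and who was told.

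The cost is one IRB-approved amendment, a rule for the envelopes and a short log. No visits, patients or measurements are added. Patients and surgeons wait longer to learn the arm: until enrollment ends, planned at about 12 weeks (Section 4), and the database is locked. The emergency provision names only the anesthesiology team and only events during or soon after surgery. The sponsor should therefore also state how a later clinical request for the allocation is handled; this review proposes no rule for that.

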## **6.2. Contraception and Pregnancy Testing**

Not Applicable

## **6.3. Study Visits and Procedures**

### **a. Screening Visits and Procedures**

After diagnosis and the decision to proceed with surgery has been made, patients will be screened for eligibility to participate in the study.

### **b. Study Visits and Procedures**

If deemed appropriate for inclusion of the study after screening, informed consent will be obtained by a research coordinator prior to proceeding with surgery

### **c. Final Study Visit:**

There is no post-operative visit required for this study.

### **d. Post Study Follow up and Procedures**

None.

### **e. Discontinuation Visit and Procedures**

Subjects who voluntarily wish to withdraw from the study will be asked to continue with all standard of care visits and procedures, and their removal from study participation will have no effect on the quality or level of care provided.

## **7. TRIAL MATERIALS**

### **7.1. Trial Product (s)**

Not Applicable

### **7.2. Storage and Drug Accountability**

Not Applicable

## **8. TREATMENT**

### **8.1. Rationale for Selection of Dose**

The dose of epinephrine has been used by the investigators in this study for several years without any reported medication-related adverse events.

### **8.2. Study Drug Formulations**

Not Applicable

### **8.3. Study Drug Administration**

Not Applicable

### **8.4. Specific Restrictions / Requirements**

No specific restrictions or requirements will be placed on the study patient except those indicated in accordance with the typical post-operative period following the specific surgical procedure that was performed.

### **8.5. Blinding**

Blinding of enrolled subjects will be performed to prevent bias from occurring based on patient expectations of the procedure. If desired, patients may learn of their study designation after completion of the surgeon-rated visual clarity score immediately post-operatively.

### **8.6. Concomitant therapy**

All medications (prescription and over the counter), vitamin and mineral supplements, and/or herbs taken by the participant will be documented.

## **9. SAFETY MEASUREMENTS**

### **9.1. Definitions**

An Adverse Event (AE) is defined as any untoward medical occurrence associated with the use of an investigational product in humans and that does not necessarily have a causal relation with the investigational product. AEs can therefore be any unfavorable and unintended sign (including an abnormal laboratory finding), symptom, or disease

temporally associated with the use of an investigational procedure or product, whether or not related to the investigational procedure or product.

An adverse event is considered “serious” if, in the view of the investigator, it results in any of the following outcomes:

- Led to death
- Led to serious deterioration in health of the subject, that either resulted in
  - o A life-threatening illness or injury, or
  - o A permanent impairment of a body structure or function, or
  - o Inpatient or prolonged hospitalization, or
  - o Medical or surgical intervention to prevent life-threatening illness or injury or permanent impairment to a body structure or a body function
- Led to fetal distress, fetal death or congenital abnormality or birth defect, or
- Required intervention to prevent permanent impairment or damage, or
- Other serious events that do not fit the other outcomes, but the event may jeopardize the subject and may require medical or surgical intervention (treatment) to prevent one of the other outcomes.

Within 48 hours of becoming aware of a SAE, the investigator must complete the SAE report (providing as much information as is immediately available). The investigator must submit this SAE report to the study’s DSMB. The investigator must also report all SAEs to the IRB, as is required by the IRB.

## **9.2. Collecting, Recording and Reporting of Adverse Events**

Adverse Events (AEs) will be collected throughout the study and all AEs will be captured. The Investigator or designee will record all AEs on the appropriate CRFs. Investigators are responsible for reporting all AEs and SAEs. The investigator will assess subjects at each study visit for the occurrence of AEs. In order to avoid bias in eliciting AEs, subjects should be asked non-leading questions. All AEs, regardless of severity, reported by the subject or found on examination or report, must be recorded. All AEs must be followed until resolution is reached. All treatments and outcomes of the AE must be recorded. All AEs and SAEs must be followed until:

- AE is resolved (i.e., return to normal/baseline values)
- Subject is lost to follow-up or withdraws consent
- Subject completes study, including required follow-up visits
- Study closure

The investigator must, following GCP guidelines, continue to treat (or refer subject to an appropriate practitioner for continuing treatment of any AE that remains unresolved after the subject has completed study participation. The severity of all AEs will be categorized as mild, moderate, or severe based on the following definitions:

- Mild: The subject is aware of the sign or symptom, but finds it easily tolerated. The event is of little concern to the subject and/or little clinical significance. The event is not expected to have any effect on the subject’s overall health or well-being.
- Moderate: The subject has discomfort enough to cause interference with or change in usual activities. The event is of some concern to the subject’s health or well-being and may require medical intervention and/or close follow-up.
- Severe: The adverse event interferes considerably with the subject’s usual activities. The event is of definite concern to the subject and/or poses substantial risk to the subject’s health or well-being. The event is likely to require medical intervention and/or close follow-up and may be incapacitating or life threatening. Hospitalization and treatment may be required.

The investigator must assess causality of AE in relation to study procedure or using of the study product as: unrelated, possible, and definite based on the following definition:

- Unrelated: The AE is definitely not associated with the study procedure
- Possible: There is evidence to suggest the causal relationship between the study procedure and the AE
- Definite: The AE was caused by the study procedure

Reporting of Adverse Events · The principal investigator will report all AEs and SAEs occurring in clinical investigations to the IRB according to the UTHSC-Houston IRB policy.

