#### **2.3. Secondary Objectives**

To evaluate mean arterial pressure, operative time, and any adverse events that occur during arthroscopic shoulder surgery.

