### **3.6. Subject Replacement**

There is no intervention or required follow-up after the pre-operative subacromial injection, so patient drop-out will be minimal.

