## 11. SAMPLE SIZE AND STATISTICAL METHODS

### 11.1. Determination of Sample Size

Thirty (n=30) subjects recruited from Texas will be sought for each group for a total enrollment of sixty (n=60). This is from a power analysis performed. The minimal clinically significant difference in visual acuity score (0-10) is 2 points, or 20%, as established in a prior study. In order to ensure 80% power at an alpha of 0.05, 26 patients are needed in each study group. Minimal attrition is expected given that there is no routine follow-up necessary.

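### Adverse events are tied to study visits that the plan does not schedule after the injection, and the safety outcome has two different windows, the wider one with no end

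*Combined protocol and SAP*

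**What the plan says.** **How events are found.** Section 9.2: "The investigator will assess subjects at each study visit for the occurrence of AEs". The same section asks for non-leading questions to subjects, and one of its end points for following events is "Subject completes study, including required follow-up visits". Section 9.3 gives a second source, clinical assessments by the principal investigator and the medical team, without a timetable.

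**What visits exist.** Section 6.3 lists screening and consent, both before surgery. Section 6.3.c then states: "There is no post-operative visit required for this study". Section 6.3.d gives no post-study follow-up. Section 3.6 says "There is no intervention or required follow-up after the pre-operative subacromial injection, so patient drop-out will be minimal", and section 11.1 says "Minimal attrition is expected given that there is no routine follow-up necessary".

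**What the outcome covers.** The secondary objective in 2.3 is "any adverse events that occur during arthroscopic shoulder surgery". The secondary outcome in the DSMP checklist of 9.3 is "adverse events intra-operatively or post-operatively". Section 5.1 also includes events after the procedure, and the checklist's data-acquisition item places adverse-event collection in the post-operative period.

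**Who knows the arm.** Section 6.1 conceals allocation from the investigator until clarity has been scored at the end of surgery. Section 8.5 adds that, if they wish, "patients may learn of their study designation after completion of the surgeon-rated visual clarity score immediately post-operatively". Section 9.2 has the investigator grade causality, and each event is also classed as mild, moderate or severe.

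**The concern.** Adverse events are a declared secondary outcome of a comparison in which epinephrine is the only planned difference between the injections, and limiting epinephrine-related cardiovascular events is part of the trial's rationale (1.2.a, 1.2.b, 2.4.b). An event count can be interpreted only if the reader knows the period observed, how events were looked for, and whether the grader knew the arm. Here the stated way of looking for events has no occasion to operate after treatment, the period is defined in two ways, and masking may have ended before grading. Two analysts following the plan could report different counts from the same patients, and a low count could be read as more reassuring than the data allow.

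**Working it through.** The plan states no adverse-event rate and no length of observation, so there is no figure to reproduce. The check is a comparison of the sections, followed by an illustration on assumed values.

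**Step 1. Does the elicitation rule operate after treatment?**

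| Encounter in the plan | Section | Relative to the injection |
|---|---|---|
| Screening | 6.3.a | before |
| Consent | 6.3.b | before |
| Final study visit | 6.3.c | no post-operative visit required |
| Post-study follow-up | 6.3.d | none |

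No study visit falls after the injection. The visit-based rule in 9.2 therefore has nothing to attach to, and neither does the reference there to required follow-up visits.

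**Step 2. What window does the outcome have?**

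| Section | Intra-operative | Post-operative | End stated |
|---|---|---|---|
| 2.3 | yes | no | end of surgery |
| 5.1 | yes | yes | none |
| 9.3 checklist, outcomes | yes | yes | none |
| 9.3 checklist, data acquisition | not mentioned | yes | none |

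Section 2.3 conflicts with the other three entries, and none of those three closes the window. The end points in 9.2 (resolution, loss or withdrawal, study completion, study closure) say how long a known event is followed. They do not say how long new events are counted.

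**Step 3. Is grading masked?** Concealment is guaranteed up to the clarity score (6.1), and patients may ask for their arm straight afterwards (8.5). Any post-operative event is graded after that point. Nothing in 9.2 requires the grader to be still unaware of the arm.

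**Step 4. Illustration of incomplete capture.** The planned group size is 30 (3.1, 11.1). The true risk p of a post-operative event per patient and the captured fraction c are assumptions. The expected count is 30 × p × c, and the chance of recording at least one event is 1 − (1 − p × c)^30.

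| p | c | Expected count | Chance of at least one |
|---|---|---|---|
| 5% | 1 | 1.5 | 79% |
| 5% | 0.5 | 0.75 | 53% |
| 10% | 1 | 3.0 | 96% |
| 10% | 0.5 | 1.5 | 79% |
| 20% | 1 | 6.0 | 99.9% |
| 20% | 0.5 | 3.0 | 96% |

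For scale, zero events among 30 fully observed patients has an exact two-sided 95% upper limit of 1 − 0.025^(1/30) = 11.6%. That limit applies only to the period in which events were actually looked for.

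**The case against.** The strongest reply is that ascertainment exists and only its timetable is missing. Section 9.2 also asks that events be collected throughout the study, including those reported by the subject or found on examination. Section 9.3 names clinical assessments as a source and says that assessments are stored in the medical record. Section 6.3.e refers to standard-of-care visits, so routine contacts do occur, and 6.3.c says only that the study itself requires no visit. On the window, three of the four places include the post-operative period, so the intended scope can be recovered. Unblinding is permitted on request and is not planned, and 6.1 does not say that investigators are told the arm after scoring. Adverse events are secondary, 9.3 calls the named cardiovascular risks very rare, and no section plans a safety claim from a zero count.

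Most of this stands, and it limits the point. It would be wrong to say that nothing but volunteered reports would reach the record. What the reply does not supply is a timetable, an end date, a common procedure for all patients, or a rule that grading precedes disclosure.

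Three stronger readings are tempting, and the documents do not support them.

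- A reader might infer from the mix of hospitals and surgery centers in the checklist that observation time will differ by site. No observation time is given for any site, and a site difference would not by itself favour an arm under randomized allocation.
- A reader might infer that events will be counted unevenly between arms. The documents make this possible, through early disclosure, but do not show it.
- A reader might inflate the 11.6% limit by some assumed capture rate. The documents give no capture rate, and events during surgery need not suffer the same loss.

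**Conclusion.** The point holds as an internal contradiction with a modest consequence. The visit-based rule in 9.2 cannot be carried out after treatment, 2.3 conflicts with 5.1 and 9.3 on the outcome's scope, and no section closes the post-operative window. Post-operative events may therefore be captured incompletely and over differing periods, and may be graded by someone who knows the arm. These conclusions about wording rest on the text alone. The size of any under-count cannot be derived from the documents, and the drop from 79% to 53% depends wholly on the assumed 5% risk and half capture. Clarity scoring and pump-pressure changes, the primary outcomes, are unaffected. The change should be made because it is cheap and the outcome is a declared one, but the trial does not stand or fall on it.

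**What to change.** - Reconcile 2.3, 5.1, 9.2 and 9.3 to one adverse-event outcome, running from the injection to one fixed end point that is the same for every patient, arm and site. Examples are recovery-room discharge, or a fixed number of days checked by chart review. A first routine clinic visit would not serve as the end point, because the documents do not fix its timing.
- In 9.2, replace assessment at study visits with that method, drawing on records that routine care already produces, and remove the reference to required follow-up visits.
- State in 6.1, 8.5 and 9.2 that severity and causality are graded before the arm is disclosed to the grader or the patient. Keep the emergency disclosure to the anesthesiology team that 5.1 already provides.

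The cost is wording in these sections, a short chart review per patient, and a later answer to patients who ask for their arm. That delay depends on the end point chosen: short if it is recovery-room discharge, longer if it is a number of days. No study visit is added.
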